 - For routine clinical care, all bariatric surgery patients undergo venipuncture for lab monitoring at 6, 9, and 12 months postoperatively. Study-specific labs will be added to these routine blood draws. The additional study-specific blood tests are needed to detect any changes (between intervention and control groups) in lipids, ALT, and/or hemoglobin A1c as a result of the medication. A pediatric CTRC research nurse will be scheduled to obtain labs at study visit 2, and at Enrollment and study visit 4 if not obtained by the clinical lab. The risks of a venipuncture include pain at the puncture site, possible bruising and edema around the puncture site, less commonly dizziness/presycope/syncope, and rarely infection.
 - DEXA scans will be performed at Visits 1 and 4 (of the total body, hip, and spine).
 The cumulative radiation exposure from these tests is considered small and is not likely to adversely affect participants. The potential risks related to the additive effect of radiation over a lifetime is included in the assent/consent.
 - Indirect calorimetry will be performed at Visits 1 and 4, and uses a canopy method.
 Potential risks include a feeling of claustrophobia, which are included in the assent/consent.
- Optional banking of specimens for future research: This is an optional procedure. For those who assent/consent, blood and urine samples will be collected at Enrollment, Visit 2, and Visit 4. DNA will be isolated from a portion of the whole blood collected at the Enrollment visit only in [name] lab at the University of Colorado Skaggs School of Pharmacy after all samples are collected. Prior to DNA isolation, the samples will be stored at -80°C. The isolated DNA will be stored at -20°C. All other blood and urine specimen, will be processed, fractionated (as appropriate), aliquoted and stored at -80°C.

3) Research-specific study visits

- Patients in the Bariatric Surgery program at Children's Colorado have several standard postoperative visits in the first year after surgery including at 3, 6, 9, and 12 months. The screening/enrollment visit will take place concurrent with the 6, 9, or 12 month postop visit whenever possible. For those with a screening/enrollment visit at 6 or 9 months, Visit 4 will typically take place concurrent with the 9 or 12 month postop visit, respectively. For those with a screening/enrollment visit at 12 months, Visit 4 will typically not be concurrent with a regularly scheduled postop visit.
- There will be a screening visit at 6, 9, or 12 months postoperatively. Eligible participants will be consented at this visit, and will be asked to come to campus ~1 week later for study visit 1. Enrollment and Visit 1 cannot be combined because it is unrealistic to screen, consent, randomize, obtain study drug, and complete additional measures after an already lengthy clinical appointment.
- The Children's Hospital Colorado Lifestyle Medicine weight management program's clinical protocols for anti-obesity pharmacotherapy require monthly clinic visits for the first three months after initiation for monitoring of effects and side effects. The proposed study protocol follows this standard.

Data Collection Tools (See Table 3. below for Schedule of Measures)

- a) Sociodemographic characteristics: age, sex, race/ethnicity, insurance, highest level of primary caregiver's education, household size and income, government-based assistance, and presence/absence of food insecurity will be obtained from the medical record and the Demographics Form.
- b) Feasibility of protocol implementation: rates of recruitment, enrollment, randomization, and dropout
- c) Study medication adherence & tolerability: assessed by 1) Questionnaire: description/dose/start date of medications, missed doses, and checklists of: effects, adverse effects, and evidence-based barriers to adherence^{51,52}; 2) Pill counts; 3) Urine amphetamine screen
- d) Self-reported changes to all non-study medications: name/dose, interim changes
- e) Patient/family satisfaction questionnaire will assess: reasons for participation, experience during study visits, satisfaction with the effect of the study medication/placebo, ease of communication with study staff, and time burden/inconvenience
- f) Biological outcome and safety measures: Weight, height, heart rate (HR), BP, basic metabolic panel, lipids, ALT, HbA1c, and pregnancy test
- g) Optional Biobanking: Gold top (serum-3.5mL blood), Purple top (EDTA-4mL whole blood), Green top (heparinized plasma-4mL blood), and Urine (volume that remains after the urine pregnancy test for females and a separate urine collection for males) will be collected with participant assent/consent for future research questions.
- h) 3-day dietary record: Participants will complete a dietary record on 3 consecutive days (2 weekday, 1 weekend day) based on standardized protocols for dietary assessment.⁵³
- i) Previous Day Physical Activity Recall (PDPAR): validated and reliable questionnaire that detects changes in physical activity behavior.⁵⁴
- j) Impact of Weight On Quality of Life-Kids & Lite (IWQOL-Kids & Lite): Kids: 27-item self (validated up to age 19) + parent-report assesses the impact of weight on: physical comfort, body esteem, social life, and family relations, and has known minimally clinically important difference scores and high test-retest reliability. 55,56 Adult (> age 20): 31-item validated tool that assesses overall, physical, self-esteem, sexual, public distress, and work. 57
- k) PedsQL: a validated measure of overall health-related quality of life
- I) Center for Epidemiologic Studies Depression Scale (CES-D): a 20-item self-report questionnaire that covers areas including depressed mood, feelings of guilt/worthlessness, helplessness, psychomotor retardation, loss of appetite and sleep disturbance over the previous week. It has good internal reliability that is robust to age, clinical vs. nonclinical setting, and risk of bias.⁴⁷

- m) Columbia Suicide Severity Rating Scale (C-SSRS): a validated, clinician-administered assessment of suicidal ideation and behavior among adolescents and adults.⁴⁸
- n) Resting Metabolic Rate: using a canopy system
- o) DEXA-3 site: total body scan to measure body composition; hip and spine scans to determine bone density, all using standardized protocols
- p) Visual Analogue Appetite Ratings (VAS): self-reported assessment of hunger/satiety before and after meals and snacks
- q) Three Factor Eating Questionnaire (TFEQ): validated questionnaire that measures cognitive restraint, uncontrolled eating, and emotional eating⁵⁸
- r) Eating in the Absence of Hunger (EAH) parent-report: validated measure that describes eating when not hungry⁵⁹

Route of Data Collection: To reduce in-person time on campus for participants, components of Study Visits 1-4 will be collected remotely (designated by superscript "R" in Table 3 below) either via secure video call or telephone call (with questionnaires emailed) in the participant's/guardian's preferred language within the same week and ideally on the same day as the study visit. These measures will be conducted remotely unless it is not possible or places an undue burden on the participant to do so (e.g. participant does not have a reliable internet connection or has a limited phone data plan that incurs significant charges). Pill count will require a video connection. All other measures require in-person collection/administration to appropriately collect outcome/safety data.

Table 3. Schedule of Measures

"X"= Study specific "O"= Standard of Care #= Bariatric Clinic or CHCO CTRC ‡= + Adult CTRC or CHCO Radiology/CTRC R= can be delivered remotely	SCREENING/ ENROLLMENT# 6-12 mo post- op	STUDY VISIT 1#,‡ ~1wk after Enrollment	STUDY VISIT 2# 4wks after Visit 1	STUDY VISIT 3# 4 wks after Visit 2	STUDY VISIT 4#,‡ 4 wks after Visit 3
Review of Inclusion/Exclusion criteria	Х				
Echocardiogram (ONLY for those with Hypertension or Severe OSA with poor PAP adherence IF not obtained in the prior 6 months)	0				
Demographics Form		X ^R			
Feasibility of protocol implementation (e.g. enrollment rates, dropout rates)	х	х	X	х	X
Study medication adherence & tolerability- Study Med Form			X ^R	X ^R	X ^R
Study medication adherence- (pill count)- Study Med Form			X ^R	X ^R	X ^R
Study medication adherence (urine amphetamine screen)		X	X	X	X
Review of all non-study medications (self-report)	Х	X ^R	X ^R	XR	X ^R
Patient/family satisfaction survey					X ^R
Weight, Height, Temperature, HR, BP; Review of Systems; Physical exam		X	Х	X	X
Urine pregnancy test	X	X	X	X	X
Lipid panel, ALT, HbA1c	Х				Х
Basic metabolic panel	Х		Х		X
Optional Biobanking	Х		Х		X
3-day diet record review		X ^R			X ^R
Previous Day Physical Activity Recall (PDPAR)		X ^R			X ^R

IWQOL-Kids (≤19yo)/-Lite (≥ 20yo) & Parent Report		X ^R			X ^R
PedsQL (general health-related quality of life)		X ^R			X ^R
CES-D (Depression Screen)	0	X	X	Χ	X
C-SSRS (Suicide Screen)	X	X	X	Х	X
Resting metabolic rate		X			X
DEXA-3 site		X			Х
Clinical Intervention/Translation Core: Eating behavior questionnaires (VAS, TFEQ, EAH)		X ^R	X ^R	X ^R	X ^R

In addition to the above in-person study visits and designated remote data collection, there are eight standard study phone calls in the protocol:

- Phone Call 1: 1-2 days before the Screening/Enrollment Visit 0 (Reminder to fast)
- Phone Call 2: 1 week before Visit 1 (Phone Call Script 1)
- Phone Call 3: 1 week after Visit 1 (Phone Call Script 2)
- Phone Call 4: 2 weeks after Visit 1 (Phone Call Script 2)
- Phone Call 5: 3 weeks after Visit 1 and 1 week before Visit 2 (Phone Call Scripts 1 & 2)
- Phone Call 6: 1 week before Visit 3 (Phone Call Script 1)
- Phone Call 7: 1 week before Visit 4 (Phone Call Script 1)
- Phone Call 8: 1 week after last dose of study drug (Phone Call Script 2)

If a participant requires additional dose titration during the protocol, the PI will conduct additional weekly phone calls until study medication dosage is stable.

E. Potential Scientific Problems:

Benchmarks for success, pitfalls, and alternatives:

Primarily, we expect this protocol to demonstrate feasibility, which will form the foundation for a larger study of pharmacotherapy as an adjunct to bariatric surgery. Secondarily, we expect to demonstrate short-term efficacy of pharmacotherapy in terms of promoting additional weight loss and improving biological markers.

Pitfalls: The perioperative bariatric surgery process is time-intensive, which may impact a family's decision to enroll/complete a study that requires three to four visits outside of routine clinical care. Each of the 4 study visits will be reimbursed at \$100/visit, with an additional possible \$50 earned at Visit 4 if pre-defined medication adherence targets are met (total \$400-\$450). Participants traveling specifically for this research study (i.e. not already traveling for a clinical reason) who live >100 miles away from the Anschutz Medical Campus, will be reimbursed up to \$300 for lodging, flight, and/or gas mileage expenses per study visit. Additionally, study medications will be provided at no cost. And, those in the placebo group may benefit relative to those not in the study because of the association between increased medical contacts and improved obesity outcomes. Our inclusion criteria combines two patient subgroups- those who do not achieve adequate weight loss and those who remain severely obese regardless of adequate weight loss. Although response to surgery is different, the ongoing risk for obesity-related morbidity is expected to be similar. Preliminary analysis of initial efficacy measures (Aims 2,3) for these two groups will be conducted to allow for detection of differences. Finally, we recognize that this "12 week" intervention includes 4 weeks of up-titration of medication. Thus, the duration on goal therapeutic doses of 16mg phentermine and 100mg immediate release topiramate is only 9 weeks. This decision was driven by the primary feasibility aim, and reduces participant burden. Depending on the outcome of this study, future studies with primary aims of efficacy and safety could prolong the duration of exposure at the goal doses of medication.

Alternatives: Given our success in using these anti-obesity medications clinically and previous experience and success of the study mentors in clinical trials, we feel confident in our ability to recruit and retain participants. However, if study numbers fall short within the timeframe of the funding, we can recruit older adolescents and young adults within the 18-24 year age range through an established relationship with the adult bariatric surgery program and Anschutz Health and Wellness Center at the University of Colorado. Regardless of the outcomes, the skills I will develop from this study will still be highly applicable to future studies. Specifically, as a PI of an investigation that uses RCT methodology, intervention development and testing, analysis, and dissemination, I would be well positioned to investigate other adjunctive perioperative therapies for severe obesity (e.g. intensive nutritional strategies).

F. Data Analysis Plan:

Sample size justification: Based on recommended practice for pilot studies, 60 the minimum sample size (10 total participants, 5 per arm) is driven by the primary aim of the study and represents a balance between participant availability (patient volume and recruitment timeline), and acceptable precision around feasibility estimates (Aim 1), which will be used for subsequent study planning. It is not based on a power calculation for group differences seen in any Aim 2 or 3 measures. To estimate precision around dropout and medication tolerability rates, we used a confidence interval approach with normal approximation of the binomial calculation 60-62. First, we estimate that a realistic dropout rate is 25%, based on 3 prior anti-obesity medication RCTs conducted in obese adolescents. 22,63,64 A realistic medication tolerability rate (% who do not discontinue medication because of adverse effects) is 85%, based on the single RCT of topiramate in adolescents and two larger RCTs of phentermine/topiramate XR in adults. ^{22,65,66} Dropout: With the minimum of 10 adolescent/young adult participants, if our observed dropout rate is 25%, we can be 68% confident that the enrollment rate estimate is accurate within 13 percentage points (or 90% confident that it is accurate within 20%). With 14 adolescent/young adult participants, if our observed dropout rate is 25%, we can be 68% confident that the enrollment rate estimate is accurate within 11 percentage points (or 90% confident that it is accurate within 18%). Medication tolerability: With 10 adolescent/voung adult participants, if our observed medication tolerability rate is 85%, we can be 68% confident that the tolerability estimate is accurate within 9 percentage points (or 90% confident that it is accurate within 16%). With 14 adolescent/young adult participants, if our observed medication tolerability rate is 85%, we can be 68% confident that the tolerability estimate is accurate within 9 percentage points (or 90% confident that it is accurate within 15%). Given possible constraints around enrollment, the level of precision with 10 or 14 adolescents/young adults was deemed acceptable to achieve protocol refinement for future RCT development.

Planned analyses: Descriptive statistics will characterize the study population. Independent samples t-tests will be performed for continuous variables and chi-square for categorical variables to determine statistically significant differences between experimental and control groups. Aim 1: Feasibility of acceptability (adherence, tolerability, and satisfaction) will be descriptively assessed using differences in proportions between experimental and control groups. Feasibility of protocol implementation will be established by determining the proportions (rates) of recruitment, enrollment, randomization, and dropout. Aims 2,3: Estimated means and variability of continuous health outcome variables (e.g. % change in weight) and intra- and intersubject variability of repeated measures (e.g. loss of control eating) will be graphically presented and visually compared for experimental vs. control groups, as this aim is not powered to run inferential statistics.

G. Summarize Knowledge to be Gained:

The goal of this study is to establish the feasibility and initial efficacy of two common anti-obesity medications for adolescents who require additional risk reduction following bariatric surgery.

Adolescents with severe obesity who don't achieve optimal weight loss and co-morbidity improvement after bariatric surgery have few evidence-based treatment options to mitigate significant health risks through the remainder of adulthood. This study has the potential for substantial impact regardless of results, given that anti-obesity medications are currently being used in the post bariatric surgery setting without an evidence base. A recent international pediatric obesity webinar (4/2019) with contributors from leading adolescent bariatric surgery centers strongly expressed need and enthusiasm for studying the role of pharmacotherapy after surgery. Our center's volume, interdisciplinary expertise, and existing IND to study these medications in this setting sets us apart as the best positioned adolescent bariatric surgery center to carry out this initial pilot, with high potential for a subsequent larger multi-site RCT to evaluate safety and efficacy, mechanism of action, and predictors of response.

H. References:

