Nausea, Vomiting, Diarrhea	DSMP				
Rare, but Serious ⁴⁰					

Acute myopia, Secondary angle closure glaucoma	DSMP
Oligohidrosis, Hyperthermia	DSMP (including temperature at every study visit)
Metabolic acidosis	Bicarbonate at enrollment, visit 2, and visit 4
Suicidal ideation/attempt	DSMP with assessment at every study visit
Fetal toxicity	Pregnancy tests at enrollment and every study visit
(Pregnancy Risk Factor Category D- positive evidence of risk)	Requirement for females to either have a LARC (majority) or documented commitment to use 2 forms of birth control
Withdrawal symptoms	Gradual discontinuation at the end of the study
Hyperammonemia and encephalopathy	Drug interaction check; DSMP
Kidney stones	BMP at enrollment, visit 2, and visit 4; Drug interaction check; DSMP
Topiramate-Ethanol interaction (potential to cause increased CNS depression)	Counseling about alcohol avoidance, and specific language about this risk in the consent/assent

Methods for systematically assessing changes in mood, suicidality, and cognition.

Mood:

Changes in mood will be systematically screened for using the Center for Epidemiologic Studies Depression Scale (CES-D). This is a 20-item self-report questionnaire that covers areas including depressed mood, feelings of guilt/worthlessness, helplessness, psychomotor retardation, loss of appetite and sleep disturbance over the previous week. ⁴⁶ This instrument has yielded adequate internal reliability that is robust to age, clinical vs. nonclinical setting, and risk of bias. ⁴⁷ The original version of the measure is appropriate for individuals 12 years of age and older. The CES-D is routinely administered to individuals receiving care at the Children's Colorado Bariatric Surgery Center at every follow-up pre-operative and post-operative clinic appointment.

The proposed study will additionally administer the CES-D at all study visits not aligned with a clinical visit and will be scored by the PI or professional research assistant. A CES-D score <20 indicates no to mild depressive symptoms. And a CES-D score ≥20 indicates elevated depressive symptoms. This is based on a metaregression that supported higher cut points having better diagnostic accuracy.⁴⁷

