Any study participant who a) newly scores ≥20 at any time during the study or b) has a baseline score of ≥20 and who demonstrates any absolute increase in this score, compared to previous measures, will be discussed within 72 hours with the Bariatric Surgery Center's pediatric clinical psychologist to consider a more comprehensive follow-up clinical interview. The clinical interview will guide additional management recommendations, which may include psychoeducation on depression, a referral to therapy, a referral to psychiatry, and/or a reduction of study medication.

Weekly phone calls after study drug start also include a question about depressed mood over the previous week and if present, ask participants to rank this as mild, moderate, or severe. If depressed mood is present and moderate or severe, the PI will discuss follow-up steps with the participant and caregiver within 24 hours of identification after consulting with study psychologist [name]; If mild and new, the PI will discuss with study psychologist [name] within 1 week of identification.

Suicidality:

Suicidal ideation and behavior will be assessed using the Columbia Suicide Severity Rating Scale (C-SSRS)^{48,49} at enrollment and each study visit. Any participant who reports suicidal behavior or suicidal ideation with some intent to act (Type 4) or with intent and a specific plan (Type 5) during the study will be discussed with the PI during *that visit*. The PI will determine whether the participant should be escorted to the Children's Hospital Colorado Emergency Department for an emergent mental health evaluation or will be discussed within 72 hours with the Bariatric Surgery Center's pediatric clinical psychologist for additional assessment/treatment recommendations.

For both mood and suicidality, if a participant's psychiatric disorder can be adequately treated with psycho- and/or pharmacotherapy, then the patient, at the discretion of the mental health provider, should be continued in the trial on randomized therapy.

Cognition:

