At 1, 2, and 3 weeks after study medication initiation, weekly during any additional titration during the protocol, and at each study visit, participants will be asked to complete a self-report checklist of possible adverse effects that have reported associations with the active study drugs, which include changes in memory, attention/concentration, word-finding/language, and overall academic/job performance, along with the perceived severity of each (mild, moderate, or severe).

Severe cognitive difficulty, which is a drug dose reduction/discontinuation criteria, will be defined as self-report of a "severe" change in memory, attention/concentration, or word finding/language that the participant believes is significantly impacting academic or job performance and that is not otherwise explained by non-study medication related factors.

Of note, in the one randomized controlled trial of topiramate for weight loss among severely obese adolescents⁵⁰ (24-week intervention of 75mg/day topiramate vs. placebo), Fox et al. found no significant differences between topiramate and placebo groups on subscales of the Cambridge Neuropsychological Test Automated Battery (CANTAB) or Behavioral Rating Inventory of Executive Function-Self Report (BRIEF-SR), and on the Connors Continuous Performance Test II (CPT II), the only significant finding was faster reaction time in the topiramate group compared to the placebo group.

2) Data and Safety Monitoring Plan (DSMP):

Definitions: The PI will use the FDA's/Center for Drug Evaluation and Research's "Guidance for Industry Investigators Safety Reporting Requirements for INDs and BA/BE Studies" document to define the terms: adverse event (AE), suspected adverse reaction, adverse reaction, unexpected, serious, and life-threatening.

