- -Comprehensive review of systems at every study visit (to capture possible AEs not reported previously)
- -Physical exam at every study visit (e.g. new murmurs, rubs, or gallops, new increased work of breathing, new pulmonary edema, new peripheral edema);
- -Vitals at every study visit (e.g. new fever, tachycardia, new elevated blood pressure/hypertension)
- -Phone call 1, 2, and 3 weeks after study drug initiation and in-person with a questionnaire at visits 2, 3, and 4 to review known possible side effects of phentermine and topiramate
- -Lab monitoring: basic metabolic panel (to assess for new metabolic acidosis: bicarb < 18 mmol/L); urine pregnancy tests for all females at every visit.
- -Monitoring of mood, suicidality, and cognition per above with validated assessments at enrollment and every study visit (e.g. new or worsened depression, new suicidal ideation/behavior)
- -Between study visits, participants with questions about symptoms will also be encouraged to call the PI directly (voicemail messages are forwarded to the PI's password-protected email)
- 3. To what external entities will local adverse events be reported?: In addition to COMIRB, the PI will report local adverse events to the FDA, according to their safety reporting requirements: https://www.fda.gov/downloads/Drugs/Guidances/UCM227351.pdf). Specifically, the PI will report to the Division of Metabolism and Endocrinology within the FDA's Center for Drug Evaluation and Research, which reviewed the IND application for this study. The PI will report to this Division: 1) Any unexpected fatal or life-threatening suspected adverse reactions no later than 7 calendar days after initial receipt of the information, and 2) Any a) serious, unexpected suspected adverse reactions, b) findings from other clinical/animal/in-vitro studies

that suggest significant human risk, and c) a clinically important increase in the rate of serious suspected adverse reactions no later than 15 calendar days after determining that this information qualifies for reporting.

4. Will periodic global review of safety/adverse events (serious adverse events and adverse events) occur?: Yes, reviews will be performed by the PI, and a three-member data and safety monitoring board (DSMB), including a primary Safety Officer.

Reviewer	Expertise	Review Frequency	Written Reports	Report Frequency

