- **5. Will any formal interim analysis be performed?:** Interim assessments of feasibility, acceptability, and safety per above will be performed, but there will be no formal interim analysis for this 12-month study.
- **6. Are there defined** participant **discontinuation criteria?**: There are no *participant* discontinuation criteria. However, there are defined *drug* discontinuation criteria as follows:
 - a) Development of an anaphylactic allergic reaction, pulmonary hypertension, evidence of new valvular heart disease, uncontrolled systemic hypertension, new arrhythmia (including persistent tachycardia), severe anxiety unresponsive to dose decrease, psychiatric disorder that cannot be adequately treated with psycho- and/or pharmacotherapy at the discretion of the study's clinical psychologist, serotonin syndrome, or pregnancy during the pharmacotherapy intervention will lead to discontinuation of phentermine.
 - b) Development of an anaphylactic allergic reaction, nephrolithiasis, severe, persistent cognitive difficulties, psychiatric disorder that cannot be adequately treated with psychoand/or pharmacotherapy at the discretion of the study's clinical psychologist, new acute myopia or secondary angle closure glaucoma, severe metabolic acidosis, hyperammonemia with encephalopathy, or pregnancy during the pharmacotherapy intervention will lead to discontinuation of topiramate.
 - c) If one medication is stopped secondary to the criteria above, the participant, if in agreement, will be continued on the other medication as monotherapy.
 - d) With consent, participants for whom one or both medications are stopped will continue to be followed according to the proposed study timeline.

7. How will the PI/research team determine if an adverse event (AE) is related to either of the study drugs?

Relatedness will be defined according to the National Institutes of Health National Institute on Aging Data Safety and Monitoring Plan Toolkit template (https://www.nia.nih.gov/research/dgcg/clinical-research-study-investigators-toolbox/data-and-safety-monitoring) as follows:

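### The CES-D rule sets no trigger for a further rise in a participant who started below 20 and has already crossed 20 on study

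*Combined protocol and SAP*

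**What the plan says.** The Mood paragraphs of section IV.D.1 set one cut point without reference to where the participant started: "And a CES-D score ≥20 indicates elevated depressive symptoms". The escalation rule then has two limbs: "a) newly scores ≥20 at any time during the study or b) has a baseline score of ≥20 and who demonstrates any absolute increase". The increase under limb (b) is judged against previous measures. Meeting either limb requires a discussion with the centre's clinical psychologist within 72 hours, to consider a fuller clinical interview. That interview may lead to psychoeducation, referral to therapy or psychiatry, or a reduction of study medication.

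Table 3 schedules the CES-D at Screening/Enrollment (as standard of care) and at Visits 1, 2, 3 and 4. The rule does not say which of the first two is the baseline.

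Other mood safeguards in the protocol are:

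- **Weekly calls (IV.D.1, Mood).** Calls after drug start ask about depressed mood. If it is moderate or severe, the PI must consult the study psychologist and discuss next steps with the family within 24 hours. If it is mild and new, the PI must discuss it with the psychologist within a week.
- **Call schedule (list after Table 3).** Script 2 calls fall 1, 2 and 3 weeks after Visit 1 and one week after the last dose. In addition, "If a participant requires additional dose titration during the protocol, the PI will conduct additional weekly phone calls until study medication dosage is stable".
- **C-SSRS.** It is given at enrollment and every study visit, with PI review of suicidal behavior or Type 4/5 ideation at that visit.
- **Adverse events (DSMP items 2 and 6).** There is review "in-person with a questionnaire at visits 2, 3, and 4 to review known possible side effects of phentermine and topiramate". New or worsened depression is an example of an adverse event. A "psychiatric disorder that cannot be adequately treated with psycho- and/or pharmacotherapy at the discretion" of the study psychologist leads to discontinuation of the drug.
- **Continuation (IV.D.1, Suicidality).** For mood and suicidality alike, staying on randomized therapy when the disorder can be adequately treated is left to the mental health provider's discretion.

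**The concern.** Limb (b) treats any worsening above the cut point as worth a discussion, but only for those who entered at 20 or more. Limb (a) sends a participant who entered lower to the psychologist on the first crossing and then has nothing further to say while the score stays elevated. The participant left without a repeat trigger is the one whose elevated symptoms appeared during the study, which is arguably the more informative pattern when looking for a drug effect on mood. Table 2 lists mood problems and suicidal ideation or attempt among topiramate's possible reactions.

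The first discussion is only to consider an interview. A participant judged at 22 not to need one would have no CES-D-driven reconsideration at 40. At stake is one safety rule giving inconsistent results. The endpoints, sample size and analysis are untouched.

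**Working it through.** The plan gives no figure to reproduce here. The check is to apply the two limbs as written to illustrative score paths.

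**Inputs.** Cut point 20 and limbs (a) and (b), from the Mood paragraphs of IV.D.1. CES-D occasions from Table 3. Call timing from the list after Table 3. Dosing weeks from section IV.C.

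**Rule as coded.** For the current score s:

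- (a) holds if s ≥ 20 and the score is newly so. Two readings were tried: no earlier score was ≥ 20, or the last score was < 20.
- (b) holds if baseline ≥ 20 and s exceeds previous measures. Two readings were tried: s exceeds the last score, or s exceeds all earlier scores.

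**Results.** The first score is baseline, and triggers are listed at the later measures.

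| Path | Rule as written | With limb (c) (see fix) |
|---|---|---|
| 15, 22, 40 | yes, no | yes, yes |
| 15, 22, 30, 40 | yes, no, no | yes, yes, yes |
| 19, 20, 45, 50 | yes, no, no | yes, yes, yes |
| 20, 21, 21, 21 | yes, no, no | unchanged |
| 20, 22, 30, 40 | yes, yes, yes | unchanged |
| 15, 22, 22, 22 | yes, no, no | unchanged |
| 15, 22, 5, 6 | yes, no, no | unchanged |

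These results are the same under both readings of each limb. The readings of (a) differ only when a score falls below 20 and crosses again. For 12, 22, 15, 24 the last score triggers if a re-crossing counts as new and does not otherwise. The point made here does not depend on that case.

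**Size of the contrast.** 21 − 20 = 1 point triggers when baseline is 20. 40 − 22 = 18 points does not when baseline is 15. With baseline below 20 and the score already at or above 20, no size of rise triggers.

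**Which visits are affected.** Visits 2, 3 and 4 fall about 4, 8 and 12 weeks after Visit 1.

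- *Visit 1 is baseline.* The earliest crossing is Visit 2, leaving Visits 3 and 4 (at most 2). Dosing continues at Visit 3. At Visit 4 phentermine stops and the topiramate taper starts.
- *Enrollment is baseline.* The earliest crossing is Visit 1, leaving Visits 2, 3 and 4 (at most 3). The week 1, 2 and 3 symptom calls precede Visit 2.

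**Do the calls fill the gap?** The scheduled Script 2 calls are at weeks 1 to 3 and one week after the last dose. The calls before Visits 3 and 4 use Script 1. The script contents are not shown. I take Script 2 to be the symptom call because its timing matches the adverse-effect calls described elsewhere in the protocol. On that basis no routine symptom call falls between Visit 2 and Visit 4 unless the dose is being re-titrated.

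**Check on the fix.** I enumerated every path on the grid 5, 15, 19, 20, 22, 30, 40 (7⁴ = 2,401 paths with four measures, 7⁵ = 16,807 with five) under all readings. Limb (c) adds no trigger at a score below 20 and none for baseline 20 or more. The most it adds per participant is 2 with four measures and 3 with five. If a re-crossing counts as new, every added trigger is a rise from a score already at or above 20.

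**The case against.** The strongest reply is that the participant is not lost to mental health care. The first crossing hands the decision on an interview to the psychologist, so 22 to 40 is a second look, whereas 20 to 21 may be that participant's first referral under the rule. The weekly-call provision is not limited to new symptoms when mood is moderate or severe, so it can require psychologist consultation repeatedly, and faster than 72 hours. If the first interview leads to a dose reduction, the resulting titration brings further weekly calls. Worsened depression calls for an adverse event form and monthly PI review. For those screened at 6 or 9 months, Visit 4 is typically also a routine clinic visit. The rule sets a minimum and bars no one from referring again.

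Much of this stands, and it rules out a stronger reading. A reader might infer that nothing else in the protocol can require a repeat psychologist contact, or that worsening mood goes unmonitored. The documents do not support either inference: the weekly-call provision does require consultation, and mood is assessed at every study visit.

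What remains is narrower. The call route depends on self-rated mood and does not routinely run between Visit 2 and Visit 4. The C-SSRS answers a different question. The visit questionnaires and adverse event recording may capture a rise but attach no psychologist discussion to it. Nor does prior contact with the psychologist explain the difference between the limbs. Participants with baseline 20 or more may also be known to the psychologist, since the clinic gives the CES-D at every follow-up appointment, yet limb (b) still applies to them.

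**Conclusion.** The gap is real on a literal reading, and its severity is minor. With baseline below 20 and a score already at or above 20, no further rise of any size sets off the CES-D rule, while a baseline of 20 or more makes a 1-point rise sufficient. The consequence is the absence of a CES-D-driven repeat discussion. It matters mainly at Visit 3 and then at Visit 4. Visit 2 is also affected if Enrollment is baseline and the crossing is at Visit 1, but the week 1 to 3 calls soften that case.

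The conclusion assumes that a score already at or above 20 at the preceding measure is not newly so, and that Script 2 is the symptom call. The documents give no rate of crossing or of further rise, so the expected number of affected participants cannot be estimated.

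**What to change.** Leave limbs (a) and (b) as they are and add: *or c) has a baseline score <20, has scored ≥20 at an earlier study measure, and now has a score ≥20 that is higher than at the immediately preceding measure.* The current-score condition prevents triggers below 20. The baseline condition leaves participants who entered at 20 or more exactly where they are. Stable or falling scores trigger nothing new.

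The cost is one clause, with no new data collection. For 14 participants the ceiling on extra psychologist discussions is 14 × 2 = 28 if Visit 1 is baseline, or 14 × 3 = 42 if Enrollment is. Reaching it would need every participant to start below 20, cross at the first later measure and rise at every visit after that, so the actual number should be small.
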